**A. PURPOSE OF THE STUDY**

The purpose of this study is to evaluate the efficacy of prophylactic antibiotics following distal/mid-shaft hypospadias repair in influencing the rate of postoperative urinary tract infection and complications.

**B. HYPOTHESIS / SPECIFIC AIMS**

We hypothesize that the use of prophylactic antibiotics following distal/mid-hypospadias repair will reduce the rate of post-operative urinary tract infection (UTI) when compared to patients not treated with prophylactic antibiotics.

**C. BACKGROUND, SIGNIFICANCE, AND RATIONALE**

Hypospadias is a congenital abnormality involving the glans, meatus and the penis, and is a common diagnosis encountered by pediatric urologists. Most often hypospadias involves the distal/mid-shaft portion of the urethra, and the only corrective treatment is surgical.

There is no consensus among pediatric urologist regarding the use of postoperative antibiotics.

The rationale for using prophylactic antibiotics is to decrease the occurrence of UTIs and complications. However, even though prophylactic antibiotics are used by some pediatric urologists, to date there has been no evidence supporting the role of prophylactic antibiotics in decreasing UTIs or complications.

Upon reviewing the literature, only one similar study was found by David Ben Meir et al. in 2004, which was a prospective study with 2 groups with and without antibiotic prophylaxis. That study included proximal hypospadias patients, which is much different than distal hypospadias in terms of outcome and complications rate. The study was also underpowered to detect a difference. They concluded that prophylactic antibiotics appeared to decrease complications and urinary tract infections but did not achieve a statistically significant difference.

**D. DESIGN AND METHODS**

This is a prospective, randomized trial involving children undergoing distal/mid-shaft hypospadias repair, age between 6 months and 2 years. Patients will be randomly assigned to two groups using a randomization method designed by CHW pharmacy; sample size of 80 patients in each group, for a total of 160 participants. Group 1 will receive prophylactic oral antibiotics following the surgery and catheter placement (Septra, 3 mg/kg), and

will continue the medication for 24-hours following catheter removal (4-8 days postoperatively). Group 2 will receive regular clinical care without prophylactic antibiotics, also including catheter placement/removal as above.

The surgical techniques used for repair of mid/distal hypospadias will be based upon individual surgeon's preference. The most frequent repairs are TIP (tabularized incised urethral plate) urethroplasty, Mathieu flip-flap and preputial flap; all of which are all well validated surgical techniques in managing such patients.

**Inclusion Criteria:**

- all children between ages 6 months to 2 years under going distal/mid shaft hypospadias repair
- children of parents who give informed consent
- English speaking
- participant must be available for follow-up 3 and 12 months post-surgery

**Exclusion criteria:**

- all proximal hypospadias and redo hypospadias repairs
- children who are allergic to sulfa medications, or are contraindicated for Septra use based on concomitant medications or G6PD deficiency based on pre-operative H&P assessment by surgeon
- patients who have UTI at time of surgery (proven by culture)

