**Measurements:**

Information from patients' medical records will also be collected for this study. This information will be about the hypospadias diagnosis, surgery, and follow-up. Data elements include: weight, age, glanular size at time of surgery, type of repair, location of hypospadias, chordee repair, days to catheter removal, urine analysis and culture results, urinary tract infection symptoms. Data will be collected into a secure RedCap™ database.

We will collect data from two urine samples for urine analysis and culture: one at time of surgery and one at time of catheter removal. These tests are standard of care for all surgical hypospadias patients. Testing will evaluate for bacteruria, pyuria, UTI and complication (fistula, wound infection, meatal stenosis) rates in both groups.

UTI will be diagnosed based on urine culture positive at 50,000CFUs per mL with one or both of the following: fever >38°C, or significant fussiness and irritability with voiding per parent report. Asymptomatic bacteriuria is known and expected in this population; therefore culture positive results alone will not be sufficient to meet the definition of UTI.

Patients in both groups will be followed up for one year following surgery to report and evaluate for postoperative complications via clinic visits already attended for regular standard of care in hypospadias patients.

**E. TOTAL NUMBER OF HUMAN RESEARCH PARTICIPANTS PROPOSED FOR THIS STUDY AT THIS SITE AND GLOBALLY. WHAT ARE THESE NUMBERS BASED ON?**

This study will include 160 participants; 80 patients in each of two groups. This number is based on current hypospadias rates available in the literature; sample size calculation, power of 0.80, p value of 0.05.

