**F. DRUGS OR PROCEDURES**

Patients will be randomly assigned to two groups: **Group 1** will receive prophylactic oral antibiotics following the surgery and catheter placement (Septra, 3 mg/kg/dose once daily), and will continue the medication for 24-hours following catheter removal (4-8 days postoperatively), and **Group 2** will receive regular clinical care without prophylactic antibiotics, including catheter placement/removal.

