### Group 1 Study Table

	Visit 1 Screening/ Surgery	Visit 2 4-8 Days Post Surgery	Visit 3 3 months Post Surgery	Visit 4 12 months Post Surgery
Study Explained/Consent	X			
Collect Urine Sample	X	X		
Administer Antibiotic	X	X		
Monitor for Adverse Events at Follow-up Clinic Visit		X	X	X

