**Key**

HD = Hard Drive

RS = Removable Storage (USB flash drive, CD, etc.)

PD = Portable Device (iPod; iPhone; PDA, etc.)

**J. PROVISIONS FOR MONITORING DATA TO ENSURE THE SAFETY OF SUBJECTS; AND ADDITIONAL SAFEGUARDS TO PROTECT THE RIGHTS AND WELFARE OF SUBJECTS WHO ARE LIKELY TO BE VULNERABLE**

Urine analysis, as part of standard clinical treatment in these patients, will provide the necessary monitoring of patient health during the study. Patients who develop a UTI will be treated with culture based antibiotics. As the use of prophylactic antibiotics varies widely between providers, patients in this study will be exposed to no more or less risk than patients receiving standard medical care.

Weekly study team meetings will take place to review patients' lab values and any other adverse events.

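### Does excluding children with a urinary tract infection at surgery fail because the culture that proves it is taken in the same visit as the first antibiotic dose?

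*Combined protocol and SAP*

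**What the plan says.** The exclusion criteria in section D list "patients who have UTI at time of surgery (proven by culture". The Measurements part of section D plans two urine samples, "one at time of surgery and one at time of catheter removal". It defines a urinary tract infection (UTI) as a culture positive at 50,000 CFU per mL together with fever above 38°C, or "significant fussiness and irritability with voiding per parent report", or both. It adds that "culture positive results alone will not be sufficient to meet the definition of UTI". Data elements to be collected include "urine analysis and culture results, urinary tract infection symptoms", with no time of recording given.

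The Group 1 table in section F puts consent, the first urine sample and the first antibiotic in one column, "Visit 1 Screening/ Surgery". The text of section F starts the antibiotic after surgery and catheter placement. Group 2 "will receive regular clinical care without prophylactic antibiotics, including catheter placement/removal"; no placebo or blinding is described. Section B states the hypothesis in terms of the rate of post-operative UTI.

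The documents do not give the time of randomisation or of the culture result. Section O defines no analysis population. Section L covers removal for safety or by the family's choice, not a late-found eligibility failure.

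**The concern.** An eligibility criterion should be settled before a child is assigned. Here the only scheduled culture that can prove the exclusion is taken in the visit where Group 1 is first dosed. If the result comes a day or more later, the exclusion acts after assignment, in a trial that describes no blinding. Section J says "Weekly study team meetings will take place to review" laboratory values and adverse events, so the team could know the arm when it sees the result.

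The UTI definition names neither a sample nor a time window. A child with a positive surgery-day culture and fever or irritability around surgery could therefore be called infected at surgery and removed, or called a postoperative UTI and counted as an event. If that choice leaned one way in Group 1 and the other way in Group 2, the comparison would be biased. Where events are few, one child can move a borderline p-value across 0.05.

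**Working it through.** **Inputs.** From the protocol: 80 children per group, 160 in all; power 0.80; significance level 0.05 (sections D and E). The protocol states no UTI rates, so the 80 per group cannot be reproduced from its own inputs. Many pairs of rates fit it (for example, 20% versus 5.5% needs about 82 per group, two-sided). Every rate below is an assumption.

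**1. Who is affected.** A positive culture without symptoms is not a UTI under the Measurements definition. If the exclusion uses that definition, only children with symptoms and a positive surgery-day culture are at issue. If their share is q, the expected number is 160 × q:

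- q = 0.5%: 160 × 0.005 = 0.8
- q = 1%: 160 × 0.01 = 1.6
- q = 2%: 160 × 0.02 = 3.2

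**2. The exclusion applied alike in both arms.** Two-sided Fisher exact test at 0.05, with power summed over all binomial tables:

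| Assumed rates (Group 2 vs Group 1) | 80 per arm | 78 per arm | Loss |
|---|---|---|---|
| 20% vs 5% | 0.793 | 0.780 | 0.013 |
| 25% vs 8% | 0.793 | 0.780 | 0.013 |
| 15% vs 3% | 0.711 | 0.695 | 0.016 |
| 10% vs 1% | 0.616 | 0.597 | 0.019 |

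Two removals per arm is four children, more than the largest expected number in step 1. Because removal turns on a culture and symptoms that precede treatment, it does not bias the comparison when done the same way in both arms.

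**3. Surgery-day infections counted as outcomes in both arms.** If a share b is infected at surgery, each event rate becomes b + (1 − b)p. For 20% versus 5%:

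- b = 1%: 0.01 + 0.99 × 0.20 = 0.208, and 0.01 + 0.99 × 0.05 = 0.060
- b = 2.5%: 0.025 + 0.975 × 0.20 = 0.220, and 0.025 + 0.975 × 0.05 = 0.074

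With the normal approximation (pooled variance, two-sided), power is 0.825 at baseline. It falls to 0.794 (b = 1%) or 0.748 (b = 2.5%) if these children are counted, against 0.821 or 0.815 if they are excluded. So the reading matters, but counting them would go against both the exclusion and a hypothesis about post-operative infection.

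**4. Uneven removal.** Suppose one Group 1 child with the event is removed and nobody is removed from Group 2:

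| Before (Group 2 vs Group 1) | p | After | p |
|---|---|---|---|
| 8/80 vs 4/80 | 0.369 | 8/80 vs 3/79 | 0.210 |
| 12/80 vs 4/80 | 0.062 | 12/80 vs 3/79 | 0.027 |
| 16/80 vs 4/80 | 0.007 | 16/80 vs 3/79 | 0.003 |

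Only the middle case changes its conclusion. Over all tables, one such removal turns a non-significant result significant with probability 0.079, 0.068, 0.118 or 0.142 for the four rate pairs of step 2, in that order. With equal true rates of 5% to 20%, the chance of a significant result favouring antibiotics rises from 0.008–0.016 to 0.027–0.032, against a nominal 0.025 in one direction.

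These figures assume a removal whenever Group 1 has any event. The chance that Group 1 holds even one ambiguous child is 1 − (1 − q)^80: 0.33 at q = 0.5%, 0.55 at 1% and 0.80 at 2%. That child would then have to be removed while a comparable Group 2 child was kept.

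**The case for a change.** The strongest argument for a change is that the remedy is nearly free. A few sentences could say that eligibility uses only what is on record before randomisation, that every child is analysed as assigned, and that only a culture taken after surgery can count toward the outcome. Irritability is a parent's report, the arm may be known, and no written rule stops one child being classified in the light of it.

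Part of this stands. The timing of randomisation relative to the culture result is unstated, and so is the handling of a late-found case. A line in the analysis notes would do no harm.

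The rest does not require a change:

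- The criterion already says that these children are excluded; only the procedure after assignment is unwritten.
- That the exclusion will act after assignment is an inference from an unstated culture turnaround and randomisation time. An earlier clinical culture is not ruled out.
- Keeping late-found cases in the analysis, rather than excluding them without knowledge of the arm, is a trade-off. It follows assignment strictly, but it leaves children already infected at surgery in the comparison. Either choice is defensible.
- Adding the surgery-day culture as a covariate in the logistic regression would mostly adjust for symptom-free bacteriuria and would not settle how a child is classified.
- A sensitivity analysis without these children would probably concern only one or two of them.

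**Conclusion.** No change is needed. The gap is a missing handling detail, and sections B and D read together point to how an analyst would fill it: the surgery-day culture serves eligibility, the catheter-removal culture serves the outcome, and late-found cases are treated alike in both arms.

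On that footing the effect is a power loss of 0.013 to 0.019, even with two children removed per arm. The larger figures, up to 0.142 for a changed conclusion, describe selective removal of a Group 1 event. They are a worst case, not weighted by how rarely an ambiguous child would arise, and the documents give no sign that such removal would occur.

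The conclusion rests on three assumptions: that the exclusion uses the symptom-based UTI definition, that few children meet it at surgery (0.5% to 2% assumed), and that any late exclusion is decided the same way in both arms from information that predates assignment.

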**Measurements:**

Information from patients' medical records will also be collected for this study. This information will be about the hypospadias diagnosis, surgery, and follow-up. Data elements include: weight, age, glanular size at time of surgery, type of repair, location of hypospadias, chordee repair, days to catheter removal, urine analysis and culture results, urinary tract infection symptoms. Data will be collected into a secure RedCap™ database.

We will collect data from two urine samples for urine analysis and culture: one at time of surgery and one at time of catheter removal. These tests are standard of care for all surgical hypospadias patients. Testing will evaluate for bacteruria, pyuria, UTI and complication (fistula, wound infection, meatal stenosis) rates in both groups.

UTI will be diagnosed based on urine culture positive at 50,000CFUs per mL with one or both of the following: fever >38°C, or significant fussiness and irritability with voiding per parent report. Asymptomatic bacteriuria is known and expected in this population; therefore culture positive results alone will not be sufficient to meet the definition of UTI.

Patients in both groups will be followed up for one year following surgery to report and evaluate for postoperative complications via clinic visits already attended for regular standard of care in hypospadias patients.

**E. TOTAL NUMBER OF HUMAN RESEARCH PARTICIPANTS PROPOSED FOR THIS STUDY AT THIS SITE AND GLOBALLY. WHAT ARE THESE NUMBERS BASED ON?**

This study will include 160 participants; 80 patients in each of two groups. This number is based on current hypospadias rates available in the literature; sample size calculation, power of 0.80, p value of 0.05.

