### Group 2 Study Table

	Visit 1 Screening/ Surgery	Visit 2 4-8 Days Post Surgery	Visit 3 3 months Post Surgery	Visit 4 12 months Post Surgery
Study Explained/Consent	X			
Collect Urine Sample	X	X		
Monitor for Adverse Events at Follow-up Clinic Visit		X	X	X

Study drug will be provided through Children's Hospital of Wisconsin research pharmacy.

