### H. RISKS AND THE PRECAUTIONS WHICH WILL BE TAKEN TO MINIMIZE RISK EXPOSURE

There is always a risk when taking any medication, including Septra, of developing adverse reactions. The adverse reaction incidence is low and usually minor, and may vary from one individual to another. Side effects that may be caused from antibiotics include:

- allergic reaction
- fever
- sore throat
- headache

- skin rash
- easy bruising or bleeding
- cough
- shortness of breath
- diarrhea
- nausea
- vomiting
- photosensitivity

Antibiotics do not guarantee that a child will not develop an infection or complication from this procedure. We will exclude all patients in which use of Septra (Sulfa medication) is contraindicated.

In the event a child needs antibiotics to treat a UTI, he will be given the appropriate treatment regardless which group he is assigned to.

The families are encouraged to report any adverse reaction, regardless of treatment arm. Contact information will be provided at time of informed consent.

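### Wound infection is a compared outcome with no criterion, counting window or suitable method of assessment, and no contact is scheduled between day 4-8 and 3 months

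*Combined protocol and SAP*

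**What the plan says.** Section A gives the purpose as the effect of prophylaxis on postoperative UTI and on complications. The hypothesis in section B concerns UTI alone, so wound infection is a complication outcome outside the hypothesis.

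Section D, Measurements, first describes the urine sampling: "We will collect data from two urine samples for urine analysis and culture: one at time of surgery and one at time of catheter removal". It then continues: "Testing will evaluate for bacteruria, pyuria, UTI and complication (fistula, wound infection, meatal stenosis) rates in both groups". UTI is defined there by a culture threshold plus symptoms. Wound infection has no definition, and the listed data elements end with urine results and UTI symptoms.

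The same part gives two broader routes by which complications can be recorded:
- Chart data: "Information from patients' medical records will also be collected for this study".
- Routine follow-up: "Patients in both groups will be followed up for one year following surgery to report and evaluate for postoperative complications via clinic visits".

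The study tables in section F set the first postoperative visit as "Visit 2 4-8 Days Post Surgery", followed by visits at 3 and 12 months. The inclusion criteria match: "participant must be available for follow-up 3 and 12 months post-surgery". The only follow-up assessment row, in both tables, is "Monitor for Adverse Events at Follow-up Clinic Visit".

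Section H, after listing the side effects of the study drug, says: "The families are encouraged to report any adverse reaction, regardless of treatment arm". Section J provides for a weekly team review of laboratory values and adverse events. Group 2 receives usual care without prophylaxis. No placebo and no masked assessor is described.

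**The concern.** Fistula and meatal stenosis persist, so examination at 3 or 12 months can find them. A wound infection is usually short-lived. One that starts after catheter removal can be treated and healed before the 3-month visit, and no scheduled assessment would then see it. Whether it is recorded depends on the family seeking care, on where that care was given, on whether the chart reached the study team, and on unprompted recall.

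Two things are at stake. Cases may be lost in both arms, which matters when few are expected among 80 children per group. Cases may also be lost unevenly, because parents know whether their child received an antibiotic and that knowledge may affect whether they call. Of the three named complications, wound infection is the one an antibiotic most directly targets, so uneven recording would do most harm here.

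**Working it through.** **Length of the gap.** The inputs are Visit 2 at day 4 to 8 and Visit 3 at 3 months (study tables, section F). Taking 3 months as 90 to 92 days (an assumption):
- shortest gap: 90 − 8 = 82 days
- longest gap: 92 − 4 = 88 days

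Most wound infections would be expected well before 3 months, so the full gap overstates the period that matters. With a counting window of, say, 30 days from surgery, the part without a scheduled visit is 30 − 8 = 22 to 30 − 4 = 26 days. Even so, most of such a window has no planned observation.

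**How each route deals with an infection that starts after Visit 2 and heals before Visit 3.**
- Urine testing: cannot detect it, and the second sample is taken at catheter removal.
- Examination at 3 or 12 months: nothing is left to see. The history may reveal it, but no question is specified.
- Medical records: capture it if care was sought and charted where the team can read it. Care given elsewhere is not addressed.
- Family report under section H: worded for adverse reactions in a passage on drug side effects, so it does not clearly cover a wound infection in an untreated child.
- Weekly review under section J: covers events the team already knows of.

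**What uneven capture could do.** The documents give no wound infection rate and no capture rate, so every figure here except the 80 per arm is assumed. Let the true risk be equal in both arms, let L be the share of infections starting after Visit 2, and let c1 and c2 be the fractions of those that are recorded in Groups 1 and 2. Infections present at Visit 2 are assumed to be fully recorded. The true risk cancels:

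observed risk ratio = (1 − L + L·c1) / (1 − L + L·c2)

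For counts, take a true risk of 6% (80 × 0.06 = 4.8 per arm) and L = 2/3, giving 1.6 by Visit 2 and 3.2 later.

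| c1 (Group 1) | c2 (Group 2) | Recorded, Group 1 | Recorded, Group 2 | Observed ratio |
|---|---|---|---|---|
| 1.0 | 1.0 | 4.80 | 4.80 | 1.00 |
| 0.5 | 0.5 | 1.6 + 1.60 = 3.20 | 3.20 | 1.00 |
| 0.5 | 0.9 | 3.20 | 1.6 + 2.88 = 4.48 | 0.71 |
| 0.9 | 0.5 | 4.48 | 3.20 | 1.40 |

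The third row is an apparent reduction of 1 − 3.20/4.48 = 29% with no true effect. It amounts to 4.48 − 3.20 = 1.28 children per arm. With the same capture rates, L = 1/3 gives 0.833/0.967 = 0.86, and L = 1 gives 0.5/0.9 = 0.56. Equal capture gives 1.00 whatever L is, and reversing the capture rates reverses the direction.

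**The case against.** The strongest reply is that the plan does have a route for complications. The sentence about testing is loosely written, but the same part of section D later assigns complications to clinic visits over one year and takes follow-up information from the chart. The adverse-event row at Visits 2, 3 and 4 can reasonably cover wound infection, and a list of data elements introduced by the word include need not be exhaustive. All of this stands.

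It also rules out a stronger reading that a reader might infer: that later infections are counted only if an unmasked family reports them. An infection treated at an unscheduled visit and charted can be counted, as can one still evident at 3 months. Section H does not support that reading either, since it is a drug-safety instruction.

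A second tempting inference is that the scheme favours the antibiotic arm. The documents do not show this. The study drug stops 24 hours after catheter removal, so being on antibiotic does not describe Group 1 for most of the gap. What remains is knowledge of the allocation, whose effect on care-seeking is unknown. The spread in Visit 2 timing (day 4 to 8) applies to both arms and shows no bias between them.

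A fair objection to the remedy is that it adds no contact in the gap and cannot recover infections for which no care was sought. That also stands and is carried into the fix as a stated limitation.

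The reply does not supply a criterion, a counting window, or a uniform way of asking about infections that have healed.

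**Conclusion.** The point holds as a weakness in how a named complication outcome is measured. Wound infection is to be compared between groups, yet it has no criterion, window or listed data element, and the sentence naming it points to urine testing. With no scheduled contact for about 82 to 88 days, a transient infection after Visit 2 enters the data only through unstructured presentation, charting or recall, in a comparison for which no masking is described.

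The consequence is a risk of under-counting and possibly of uneven counting. The illustrative ratios, from 0.56 to 1.40, rest wholly on assumed capture rates and late-onset shares, and none of them estimates a bias in this trial. The point rests on two assumptions: that some wound infections start after catheter removal and heal before 3 months, and that families know their allocation because Group 2 receives no placebo. It does not affect the definition of UTI, on which the hypothesis rests.

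**What to change.** 1. Correct section D, Measurements, so that urine testing covers bacteriuria, pyuria and the culture part of the UTI definition, while fistula, wound infection and meatal stenosis are assessed by examination and history at Visits 2, 3 and 4 in both arms. Add a matching row to both study tables and a dedicated database field.
2. At Visit 3, ask every family in both arms the same scripted question: any wound redness, pus or swelling since surgery, with the date, whether care was sought, and where.
3. Count wound infection as a clinician diagnosis within a fixed window from surgery (for example, 30 days), confirmed from the record where care was given.
4. Report symptoms without care-seeking separately by arm, so that a difference in care-seeking can be seen.

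The cost is a corrected paragraph, one table row, one field, one question at an existing visit, and requests for outside records. No visit is added and treatment is unchanged. The downsides are recall over about 3 months, only partly offset by checking records, and any difference in care-seeking between unmasked arms, which these steps make more visible but do not remove. The plan should state both as limitations.
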